## Protocol Title:

Hemodynamic effects of blood flow variation in continuous renal replacement therapy

Hemodynamic data: blood pressure, heart rate, and vasopressor dose will be documented. If the patient's primary care team has prescribed a device for cardiac output monitoring, stroke volume will also be documented.

Period 1: CRRT will be administered with blood flow rate (BFR) of 150 ml per minute. Hemodynamic data will be documented every minute for 10 minutes

Period 2: BFR will be increased to 350 ml per minute. Hemodynamic data will be documented every minute for 10 minutes.

Period 3: BFR will be decreased back to 150 ml per minute. Hemodynamic data will be documented every minute for 10 minutes.

Blood flow rate changes will be made at approximately one minute intervals in increments of no more than 75 mL/min.

After the third study period, patients will be monitored with the ICU nurse at the bedside and the attending physician immediately available for additional 10 minutes.

After the completion of all three study periods, BFR will be returned to the level prescribed by the clinical nephrology team caring for the patient, determined by standard of care.

c) If the proposed study is a clinical trial where a drug, vaccine, device or other treatment is compared to a placebo group or comparison treatment group, what are the guidelines or endpoints by which early decisions regarding efficacy or lack of efficacy can be made? For example, it may be reasonable to stop enrollment on a study when efficacy has already been clearly demonstrated, to avoid unnecessary enrollments of additional subjects. Alternatively, it may be reasonable to stop enrollment when it is clear that efficacy will never be demonstrated, given the statistical power of the study as designed. Describe the guidelines that are in place to assist in making these determinations, if relevant to the proposed study.

NA

d) Describe how data analysis will be performed (statistical tests, methods of evaluating data) and indicate the smallest group/unit for which separate reporting will occur. For studies involving a questionnaire, if data and reliability information are available, please describe or provide references. For full board, unfunded studies describe sample size determination and power analysis. If none, please justify.

Changes in blood pressure, heart rate, stroke volume, and vasopressor dose will be studied with paired t-tests. Based on prior studies of patients with sepsis, short-term variability of systolic blood pressure is about  $6\% \pm 4\%$  (Tavernier 1998, Michard 2000) after patients have received volume expansion. Taking this difference in blood pressure as the minimum clinically important difference, a sample size of about 12-15 patients will be needed for a power of 0.9 and  $\alpha$  of 0.05 to show a 6mm or greater difference in blood pressure.

Please save frequently

e) State if deception (including incomplete disclosure of study purpose/procedures) will be used. If so, describe the nature of the deception and provide a rationale for its use. Also, describe debriefing procedures or justify a waiver of the requirement to debrief. NOTE: for studies using deception, an alteration of consent must be justified in the Informed Consent section of the protocol (#13) and the debriefing script/statement must be uploaded in the Attachments section

Protocol Title: Hemodynamic effects of blood flow variation in continuous renal replacement therapy

---

(#16). See IRB Deception Guidelines.

f) Is there an accepted standard of care and/or standard practice at SLU for the condition/disease/situation being studied? This information will assist in comparing the risk/benefit ratio of study procedures relevant to usual care that would be received outside of the research context. \*?HELP?\* Y

If yes, please describe the standard of care and standard practice at SLU for the condition/disease/situation being studied.

All portions of the experimental protocol are within standards of care. The NxStage Cartridge Express device is approved for blood flows from 50-600 ml per minute. We will be studying blood flows within this range. The usual blood flow rate prescribed at Saint Louis University Hospital is 200-300 ml per minute. The dialysate flow rate and composition will be determined by standards of care and the judgment of the nephrology consult attending physician, and will not be altered in the study.

There are no studies or manufacturer guidelines establishing how quickly blood flow should be changed. When the prescribed blood flow rate is changed, standard nursing practice in Saint Louis University Hospital medical intensive care unit is to change blood flow settings in a single step. As a cautionary measure, blood flow rate changes will be made at approximately one minute intervals in increments of no more than 75 mL/min.

g) Does this study involve any diagnostic imaging, labwork or genetic testing that could result in clinical discovery (diagnoses, genetic mutations, etc.)? Note that this could include discovery that is expected (related to the research) or incidental (not related to research aims, but possible, like a mass/shadow found in imaging despite not looking for it). N

If yes, please describe and include whether there are plans to share findings with study participants.

h) Is this study subject to the NIH Genomic Data Sharing Policy? N

The NIH GDS policy applies to all NIH-funded research that generates large-scale human genomic data as well as the use of these data for subsequent research and includes: genome-wide association studies (GWAS), single nucleotide polymorphisms (SNP) arrays, and genome sequence, transcriptomic, metagenomics, epigenomic and gene expression data, irrespective of NIH funding mechanism. Click here for more specific examples.

---

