**b) List your research objectives (specific aims & hypotheses of the study).**

Hypothesis:

We hypothesize that within the range of BFR currently used, and at a fixed dialysate flow rate, the impact of BFR in the CRRT machine on patient's hemodynamics will be clinically insignificant, as defined as a change in systolic blood pressure of less than 6mm mercury (see section 3d).

Specific Aims:

The goal of the study is to estimate the change hemodynamic parameters that occurs (if any) when blood flow is varied in the range specified above.

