**Please save frequently**

Page numbers from a sponsor's protocol/grant may be referenced in 3b, 3c, and 3d.

b) Describe all the procedures, from screening through end-of-study, that the human subject must undergo in the research project, including study visits, drug treatments, randomization and the procedures that are part of standard of care. Specify which procedures are for research and which are standard of care. Please note: The box below is for text only. If you would like to add tables, charts, etc., attach those files in the Attachment section (#16).

Screening: subjects on CRRT who are on the medical ICU service will be screened for inclusion and exclusion criteria.

Informed consent: Consent will be obtained from patients or a health care proxy (in cases where patient does not have capacity to give consent) in a private room. The consent process is detailed in section 8d of this submission and attached consent form.

The study procedure and enrollment of patients receiving CRRT through the division of Nephrology at Saint Louis University has been approved by division chief [name]. [name], director of the medical ICU, is a coinvestigator and has approved the protocol and enrollment of eligible patients on the MICU service. When a patient is enrolled in the study, [name], a coinvestigator and faculty member with the division of Nephrology, will ensure that CRRT orders reflect the study protocol. The ICU physician conducting the study protocol will ensure that if the patient is prescribed vasopressors, titration orders are modified to reflect the study protocol; vasopressor dose will remain constant as long as blood pressure remains within the protocol-specified parameters, but may be titrated if patients develop any pre-specified safety endpoints, adverse reactions or at physician discretion if clinically indicated. If a patient is enrolled, this will be communicated to the physicians on nephrology consult and the medical intensive care unit teams caring for the patient. All study procedures are consistent with FDA-approved uses of the dialysis device and are within established standards of care.

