Procedure: An attending or fellow physician who is a member of the investigator team will supervise the entire protocol at the bedside. An ICU nurse will be present during the protocol. The study physician will ensure that patient's MAP is  $\geq 65$  mm Hg prior to initiating protocol. The study protocol is divided into three periods, each lasting 10 minutes. During all three periods, dialysate flow rate will be as prescribed by the nephrology consult attending physician, and fluid removal will be set to minimal.

The pre-specified protocol BFR rates of 150 and 350 ml/min were chosen because these are values at the lower and higher end of standard of care, respectively, and the range outside of which circuit lifespan observational studies suggest circuit lifespan may decrease (Dunn 2014). The protocol consists of two separate periods of BFR set to 150 in order to account for the influence of time on hemodynamics, separate from the influence of BFR. To clarify, if hemodynamics change from period 1 to period 2, it will not be clear if this is due to change in blood flow or changes over time. Repeating measurements at low blood flow will permit estimation of time-dependent effects. Large randomized trials involving the use of CRRT have used blood flows similar to those being studied in this protocol (Vinsonneau 2006, Palevsky 2008).

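### Section 3d does not say which periods are compared or how the repeat period at 150 ml/min enters the blood-flow estimate, although section 3b adds that period to account for time

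*Combined protocol and SAP*

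**What the plan says.** Every patient has the same order: 150, then 350, then 150 ml/min, 10 minutes each, with readings every minute (section 3b). Section 2c describes the study as a non-randomized cross-over.

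Section 3b gives the reason for the third period: "The protocol consists of two separate periods of BFR set to 150 in order to account for the influence of time on hemodynamics". Of a change between Periods 1 and 2 alone, it says that "it will not be clear if this is due to change in blood flow or changes over time". It then says: "Repeating measurements at low blood flow will permit estimation of time-dependent effects".

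Section 3b also limits some sources of drift: "vasopressor dose will remain constant as long as blood pressure remains within the protocol-specified parameters", and "fluid removal will be set to minimal".

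Section 3d holds all of the analysis text: "Changes in blood pressure, heart rate, stroke volume, and vasopressor dose will be studied with paired t-tests". It adds a sample-size statement: "a sample size of about 12-15 patients will be needed for a power of 0.9". It names no pair of periods, no summary of the ten readings per period and no role for Period 3. The hypothesis in section 2b is that the effect is clinically insignificant, "as defined as a change in systolic blood pressure of less than 6mm mercury".

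**The concern.** With one fixed order, time is not balanced by design, so only the analysis can separate it from blood flow. Section 3b recognises this and collects the data needed, but section 3d does not carry the idea into an estimate.

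Two obvious paired tests are open, Period 2 against Period 1 and Period 2 against Period 3. Under a shared linear drift they estimate different quantities, and no rule says which one counts. A separate test of Period 3 against Period 1 would show drift but would leave the blood-flow estimate uncorrected.

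At stake is the estimate that will be read against the 6 mmHg limit. Drift could create an apparent effect or hide a real one, and the comparison could be chosen after the results are seen.

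**Working it through.** **Inputs.** From section 3d: 6 mmHg, power 0.9, alpha 0.05 and 12 to 15 patients. Not in the documents: the SD of the paired difference in mmHg, the sidedness of alpha (two-sided assumed) and the size or direction of any drift. The drift values below are assumptions.

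**1. The plan's own figure.** For a paired t-test using the noncentral t, with noncentrality 6√n / SD, power is exactly 0.9 at SD 5.83 mmHg for n = 12 and at SD 6.66 mmHg for n = 15. An SD of 6 needs n = 13. The stated sample size is therefore consistent with a paired SD near 6, which is used as the base case. An SD of 10 is shown as a wider case.

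**2. Bias by comparison.** Let b be the flow effect and g the average drift per period. The expected period means are P1 = μ, P2 = μ + b + g and P3 = μ + 2g. Then:

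- P2 − P1 has expectation b + g
- P2 − P3 has expectation b − g
- P3 − P1 has expectation 2g, with no information on b
- P2 − (P1 + P3)/2 has expectation b + g − (0 + 2g)/2 = b

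The two single-period comparisons differ by 2g. With b = 6 and g = 3 they average 9 and 3, on opposite sides of the limit.

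**3. Rejection of zero when b = 0, P2 against P1.** Noncentrality is g√n / SD. For example, g = 2, SD = 6 and n = 12 give 2 × 3.464 / 6 = 1.155, and rejection 0.184.

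| g (mmHg per period) | SD 6, n = 12/15 | SD 10, n = 12/15 |
|---|---|---|
| 0.5 | 0.058 / 0.060 | 0.053 / 0.054 |
| 1 | 0.083 / 0.092 | 0.062 / 0.065 |
| 2 | 0.184 / 0.225 | 0.097 / 0.112 |
| 3 | 0.353 / 0.438 | 0.158 / 0.192 |

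In simulation the averaged contrast rejected in about 5% of trials under linear drift.

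**4. Drift must be shared.** Adding to SD 6 a patient-level drift with mean zero and SD 3 mmHg (n = 13, 40,000 simulated trials) gave 4.9% rejection. Such drift widens the SD but does not bias P2 − P1.

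**5. Precision of the contrast.** Let r be the correlation of Period 2 with each 150 ml/min period and r13 that of Periods 1 and 3. With equal variances, the ratio of the contrast SD to the pairwise SD is √[(1.5 + 0.5·r13 − 2r) / (2(1 − r))]. This is 0.866 if r13 = r, 0.935 at r = 0.8 and r13 = 0.9, and 1.0 at r = 0.8 and r13 = 1. At a pairwise SD of 6 without drift, power for 6 mmHg is 0.88/0.95 pairwise (n = 12/15), against 0.95/0.99 at ratio 0.866 and 0.92/0.97 at ratio 0.935.

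**6. Where the contrast fails.** If a shift of 2 mmHg falls wholly between Periods 1 and 2, the bias is 2 in P2 − P1, 0 in P2 − P3 and 1 in the contrast. If it falls wholly between Periods 2 and 3, the biases are 0, −2 and −1. If a residual effect c of 350 ml/min persists through Period 3, the contrast has expectation b − c/2, whereas P2 − P1 is untouched by c.

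**The case against.** A reader might infer that the plan commits to Period 2 against Period 1, or that any paired test of Period 2 carries drift. The documents do not support either. Section 3d never names that comparison, section 3b warns against relying on it, and a paired t-test of Period 2 against the mean of Periods 1 and 3 fits the wording of 3d. The fault is the unnamed contrast, not the t-test. A paired test of Period 3 against Period 1 would also meet the narrow promise to estimate time effects, though it would not adjust the flow estimate.

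The size of the harm is also open. Bias needs a drift in the same direction across patients, and nothing in the documents gives one. The three periods last 30 minutes in all, with vasopressor dose held constant within limits and minimal fluid removal.

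Rejecting zero is, moreover, not the same as crossing 6 mmHg. With no flow effect and SD 6, P2 − P1 itself exceeds 6 mmHg in only about 1% of trials or fewer at g = 2, and in 4.2%/2.6% at g = 3 (n = 12/15). Against that, at n = 12 the chance that the whole 95% CI lies within ±6 falls from 0.77 without drift to 0.55 at g = 2.

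Finally, using Period 3 is not uniformly better. It can bring in carry-over that P2 − P1 does not contain, and this shrinks the estimate toward the investigators' hypothesis.

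All of this limits the claim. What stands is that the protocol itself treats time as a threat, adds a period to deal with it, and then does not say how that period is used.

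**Conclusion.** The point holds as a gap between the stated purpose of the design and its analysis. It does not show that the study is invalid or that a wrong test was chosen.

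If 3d is carried out with a single-period comparator, a shared drift of g per period enters the estimate in full, with a sign that depends on the comparator. The effect on rejection of zero is near nil at 0.5 mmHg, modest at 1 mmHg and material from about 2 mmHg at SD 6. It is smaller at SD 10. These figures are conditional on a common linear drift and an assumed SD, neither of which the documents give. The change is worth making because it is cheap, uses data already planned and delivers what section 3b sets out to do.

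**What to change.** In section 3d:

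- **Primary estimate:** for each patient, mean systolic pressure in Period 2 minus the average of the Period 1 and Period 3 means. Test it with a one-sample (paired) t-test and report it with its 95% CI against the 6 mmHg limit.
- **Readings used:** the same minutes in each period, after target flow is reached. Going from 150 to 350 ml/min in steps of at most 75 takes three steps (200/75 = 2.67) about a minute apart, so some early readings may be at intermediate flow.
- **Drift check:** Period 3 minus Period 1, with its CI.
- **Sensitivity analysis:** Period 2 minus Period 1, because it is free of carry-over from 350 ml/min. State also that this is the fallback, flagged as unadjusted for time, if Period 3 is missing.
- **Other outcomes:** the same contrast for heart rate, and for stroke volume where it is measured. Summarise vasopressor dose descriptively, since it is held constant unless titrated, and flag systolic readings taken after a titration.

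The cost is a few sentences, with no extra patients or measurements and a few early readings unused. The downside should be stated in the plan: the contrast removes linear drift only (half of a one-step shift remains), and a residual effect c in Period 3 shrinks it by c/2, toward the hypothesis of no important effect.

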**Please save frequently**

**c) Describe the study design (e.g., single/double blind, parallel, crossover, control, experimental, observational, etc.). If the study is investigator-initiated, a timeline for individual subject recruitment, follow-up, and analysis for the study is required. Also, indicate if the subjects will be randomized.**

Prospective, cross-over, non-randomized study.

Timeline:

Recruitment: 18 months

Follow-up: subjects will be monitored for the 30 minutes during study protocol and for an additional 10 minutes. As this is a physiological study using an FDA-approved device being used in an FDA-approved manner after the clinical decision has already been made to institute therapy, long-term followup will not be required.

Analysis: Data analysis and publication will take one year after study is completed.

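### Does the missing reference systolic pressure in section 3d leave the 12-15 patient sample size too small for a 6 mm change?

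*Combined protocol and SAP*

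**What the plan says.** The hypothesis in section 2b is that the effect of blood flow rate is "clinically insignificant, as defined as a change in systolic blood pressure of less than 6mm mercury (see section 3d"). Section 3d says that "short-term variability of systolic blood pressure is about" 6% ± 4%, citing studies of patients with sepsis after volume expansion. It continues: "Taking this difference in blood pressure as the minimum clinically important difference, a sample size of about 12-15 patients will be needed", at power 0.9 and alpha 0.05, "to show a 6mm or greater difference in blood pressure". The test is given as follows: "Changes in blood pressure, heart rate, stroke volume, and vasopressor dose will be studied with paired t-tests".

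The only pressure level in the text is an entry condition in section 3b, "The study physician will ensure that patient's MAP is" at least 65 mm Hg. For each of the three periods, section 3b also states: "Hemodynamic data will be documented every minute for 10 minutes".

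The text supplied does not state the SBP at which 6% was taken as 6 mm, the SD of the within-patient change, or whether the test is one- or two-sided.

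**The concern.** A paired t-test is sized from the ratio of the target change to the SD of the within-patient change. Here the target is in mmHg and the variability is in percent. The two can be combined only at a known pressure, and 6% equals 6 mm only at SBP 100. If the patients' mean SBP is higher and the SD scales with it, the SD in mmHg rises while the 6 mm target stays put, and 12-15 patients would give less than the stated power.

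The direction of the hypothesis sharpens this. The investigators expect a change below 6 mm, so a real 6 mm change missed for lack of power could be taken as support for their view. At an assumed mean SBP of 120, under the two SD readings used below, the chance of missing it would be 20-25% with 12 patients and 11-15% with 15, against the 10% that section 3d implies.

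**Working it through.** **Inputs from section 3d.** Paired t-test; target change 6 mm; alpha 0.05; power 0.9; variability 6% ± 4%; stated size 12-15.

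**Assumptions.** Two-sided testing unless noted. The SD of the within-patient change is read in two ways:

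- Reading A: SD = 0.06 × SBP.
- Reading B: SD = 0.04 × √2 × SBP (4% per value, two uncorrelated values).

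The SBP range is also an assumption.

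**Formula.** Power is taken from the noncentral t distribution with n − 1 degrees of freedom and noncentrality (6/SD) × √n. The required n is the smallest that gives power of at least 0.9.

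**Step 1: reproduce the plan's figure.** At SBP 100, where 6% is 6 mm:

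- Reading A: SD = 0.06 × 100 = 6.00, so 6/SD = 1.00 and n = 13.
- Reading B: SD = 0.04 × 1.414 × 100 = 5.66, so 6/SD = 1.06 and n = 12.

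Both fall within 12-15. If target and SD are both kept in percent, the ratios are the same (6/6 and 6/5.66), so n is 13 or 12 at any pressure.

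**Step 2: vary SBP with the target fixed at 6 mm.**

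| SBP | SD, A | n, A | SD, B | n, B |
|---|---|---|---|---|
| 90 | 5.40 | 11 | 5.09 | 10 |
| 100 | 6.00 | 13 | 5.66 | 12 |
| 110 | 6.60 | 15 | 6.22 | 14 |
| 120 | 7.20 | 18 | 6.79 | 16 |
| 130 | 7.80 | 20 | 7.35 | 18 |

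At SBP 120, power is 0.75 (A) and 0.80 (B) with 12 patients, and 0.85 (A) and 0.89 (B) with 15.

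**Step 3: how far the stated size stretches.** The largest SD that keeps 0.9 power is 5.83 mm with 12 patients and 6.66 mm with 15. For 15 patients this is SBP 6.66/0.06 = 111 under A, or 6.66/(0.04 × 1.414) = about 118 under B.

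**Step 4: other choices the text permits, all at SBP 120.**

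- One-sided exact t: 14 (A), 13 (B).
- SD of the change 4%: 9.
- SD of the change 6% × √2: 33.
- Means of the ten readings per period, SD = k × √2 × √((1 + 9ρ)/10) × 120. With ρ = 0.5, k = 4% gives SD 5.03 and n = 10, and k = 6% gives SD 7.55 and n = 19. With ρ = 0.3, k = 4% gives SD 4.13 and n = 8, and k = 6% gives SD 6.19 and n = 14.

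The choice of SD reading moves n from 9 to 33 at one fixed pressure. Moving SBP from 100 to 120 within a reading moves it by 4 or 5.

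**Step 5: precision at SBP 120 under the less favourable of readings A and B.** With SD 7.2, the half-width of a two-sided 95% interval for the mean change is 2.201 × 7.2/√12 = 4.6 mm with 12 patients and 2.145 × 7.2/√15 = 4.0 mm with 15.

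**The case for a change.** The strongest case for a change is that the SD of the within-patient change is the one quantity a paired sample size cannot do without, and it is absent. The form asks for a power analysis. The entry condition sets a floor on mean arterial pressure, and nothing in the supplied text caps SBP, so a mean of 120 is not excluded. Recasting the aim as equivalence does not help: two one-sided tests with a 6 mm margin and a true change of zero need the same 16 and 18 patients at SBP 120. Neither one-sided testing nor averaging of readings is written into the plan, so neither can be claimed in its defence. Stating the missing inputs would take one paragraph.

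The omission stands, and so does the arithmetic. What does not follow is that the study is undersized. Nothing in the documents makes 120 likelier than 100. The patients are in a medical ICU on continuous renal replacement therapy, some on vasopressors, and the plan's own equation of 6% with 6 mm points to 100. Reading 6%, or 4% × √2, as the SD of the change, and as proportional to pressure, is a construction placed on a cited figure whose meaning cannot be checked here. Misreading a non-significant t-test as proof of a small change would be an error at any SBP; it does not arise from the missing reference pressure.

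**Conclusion.** No change is needed. Section 3d under-reports its assumptions, but its number is coherent: with 6% taken as 6 mm, 12 or 13 patients give 0.9 power under readings B and A, and 15 patients hold that power up to an SD of the change of about 6.6 mm. The shortfall at SBP 120 is 1 patient beyond the upper end of the stated range under one reading and 3 under the other. It needs a pressure the documents do not give, a two-sided test they do not specify, and no benefit from ten readings per period.

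Writing the SD, reference SBP and sidedness into section 3d would document a figure that already reproduces and would alter neither the design nor the analysis. Enrolling 18 patients would rest on the less favourable of two assumed SDs at an assumed pressure. Section 2b sets out to estimate the change, and the interval that comes with a paired t-test will show the precision reached, whatever SD was assumed at planning. Even with SD 7.2, that interval is narrower than ±6 mm with 12 patients.

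This conclusion rests on the SD of the within-patient change being near readings A or B, or smaller. If it were as large as 6% × √2, 12-15 patients would be too few even at SBP 100, where 24 would be needed; nothing in the documents supports that reading over the two that reproduce the plan's figure.
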